6.5.13 Clinical responses

Participants will be asked to score their previous and current hay fever symptoms at different time points before and during treatment (Appendix 1 – 4). During the season symptoms and rescue medication scores will be assessed weekly (Appendix 3, 5).

Questionnaires will be either all filled out on paper (Appendix 1-5) or all via a computerized version of the questionnaires. In case of the latter, SurveyAnalytics (Survey Analytics LLC, Seattle, Washington) will be the web-based service used. This is a service for conducting surveys and facilitated data collection. Surveys created are owned solely by the administrator of that survey. The application allows password protection and uses secure encryption. Email addresses uploaded to the system for the purpose of sending survey invitations and email communication and the collected data are owned solely by the survey administrator and not divulged to a third party.

6.5.14 Visits

Atopic Participants:

Scheduled Visits (screening, randomisation and blinded treatment phase):

Where possible, all study visits should occur within the time limits specified below:

Screening Visit – Visit -1, from December 2013 to April 2014.

Visit – 0a, after screening and before Visit 0b.

Visit – 0b, from January 2014 to April 2014.

Visit – 1, after Visit – 0b.

Visit – 2, from February to May 2014.

Visit – 3, from March to May 2014.

Visit – 4, from April to June 2014.

Visit – 5, from May to August 2014.

Visit – 6, from July to October, 2014

Visit – 7, from January to April 2015.

Unblinded treatment phase

Visit- 8, January-March 2016

Visit- 9, January-March 2017

Unscheduled visits:

Unscheduled visits may be performed in the event that participants experience a disease exacerbation requiring treatment or because the participant prematurely terminates from the study (see section 6.3.3).

Visit -1:**Screening visit:**

Volunteers will attend the allergy unit at the Royal Brompton Hospital for approximately 2 hours. During this visit the following will be undertaken:

- Written informed consent before any study procedures are performed.
- Demographic data (sex, date of birth, ethnic origin, medical history).
- Allergic history - record of allergic symptoms and allergic medication taken by the subject during at least the last two years.
- Physical examination and observations (weight, height, blood pressure, heart rate, peak expiratory flow rate, peak nasal inspiratory flow and spirometry).
- Participants will mark a retrospective Global evaluation (GE) visual analogue scale (VAS) (scale 0-100 mm; **Appendix 1**) and complete a retrospective GE chart (**Appendix 2**) documenting the overall severity of their hay fever symptoms during the previous pollen season.
- Participants will complete a Mini Juniper Rhinitis Quality of Life Questionnaire (mRQLQ) (**Appendix 3**) and Global evaluation scores (**Appendix 4 and 5**) corresponding to current rhinitis symptoms and medications.
- Skin prick test - standard allergen test panel as described previously.
- Blood sampling of up to 20 ml for total IgE, specific IgE to Timothy grass pollen and total blood count will be taken.
- Nasal challenge with 5,000 BU/ml Timothy grass pollen extract with TNSS recorded after 5 minutes (**Appendix 6**).
- Recording of concomitant medication.
- Evaluation of inclusion and exclusion criteria.

Visit 0a:

1st Baseline Visit:

Volunteers meeting the inclusion and exclusion criteria will be randomised into the two arms and will come in for 60 minutes for blood sampling (120 ml), nasal lavage (wash), nasal brushings and nasal fluid collections.

Table 1: Visit 0a

Time (hr:min)		Procedure
00:00	Arrival	
00:05	Blood sampling	120ml peripheral blood
00:15	Pre-lavage	Secretion collection
00:20	Pre-lavage	Nasal brushings
00:25	Nasal-lavage	
00:55	Post-lavage	Secretion collection

Visit 0b:**2nd Baseline Visit:**

On the 2nd baseline visit participants will attend the allergy unit for a period of 2 hours in the morning and 1 hour in the evening (overall 3 hours). During this visit the following will be undertaken (see also **Table 2**):

- A period of 15 minutes acclimatization to hospital environment and relative inactivity.
- Participants will receive a nasal wash (lavage).
- Duplicate intradermal injections of 1.0 BU timothy grass allergen into the extensor surface of their right and left forearm, and a saline control injection also on the right arm will be performed. The EPR will be recorded at 15 minutes after injection; the LPR will be measured at 8 hours after injection.
- The participants will receive a nasal allergen challenge with 5,000 BU/ml Timothy grass pollen extract. The EPR after the nasal challenge will be recorded

via the TNSS score (**Appendix 6**) and VAS score (**Appendix 7**) before challenge and after 5, 15, 30 and 60 minutes.

- Peak nasal inspiratory flow (PNIF) will be assessed shortly before collecting the nasal fluid before the nasal challenge and after 5, 15, 30 and 60 minutes after the nasal challenge.
- Peak expiratory flow (Peak Flow) will be assessed before nasal allergen challenge and 60 minutes after nasal allergen challenge.
- Nasal fluid will be collected by inserting a single foam sponge into each nostril and will be left in place for 2 minutes before removal. Secretions will be collected before challenge, at 5, 15, 30 and 60 minutes after nasal challenge and after 8 hours.
- The volunteers are allowed to leave the hospital (e.g. for work) and will return in the evening (after 8 hours) to allow reading of the skin LPR. Additionally, volunteers will undergo nasal brushings on both sides and a nasal biopsy. After the biopsy, volunteers will be observed for a further 30 minutes to ensure there is no nasal bleeding, and then allowed home.
- Food and non-caffeine-containing beverages (at room temperature) will be provided to all participants.

Table 2: Time line procedures at Visit 0b

Time (hr:min)	*Participants will be allowed to leave and return at 8hours	Procedure
00:00	Arrival	
00:15	Pre Lavage	Secretion collection
00:20	Nasal Lavage	Nasal lavage with 240 ml SinuRinse solution
00:25	Intradermal test	1BU intradermal inject to left and right forearm + saline injection
00:40	Intradermal test	EPR recorded at 15 minutes
00:50	Pre-Challenge	TNSS + VAS, PNIF, Secretion collection

00:55	Nasal Challenge	5,000 BU/ml Timothy grass pollen allergen
01:00	Early Nasal response	TNSS + VAS; PNIF; Secretion collection
01:10	Early Nasal response	TNSS + VAS; PNIF; Secretion collection
01:25	Early Nasal response	TNSS + VAS; PNIF; Secretion collection
01:55*	Early Nasal response	TNSS + VAS; PNIF; PeakFlow; Secretion collection
08:25*	Intradermal test	LPR
08:30		Secretion collection Nasal brushings Nasal biopsy

TNSS; total nasal symptom score

VAS; visual analogue scale

EPR; Early phase response

LPR; Late phase response

BU; Bioequivalent Unit

PNIF; Peak nasal inspiratory flow

Visit 1:

Initiation of treatment will take place after Visit 0 including an inspection of the nasal biopsy site. The patients will be required to remain for 60 minutes in the hospital after intake of the first AIT/Placebo.

Visit 2, 3 and 4:

After around 4, 8 and 12 weeks of treatment starting the tablets (AIT/placebo), participants will return during the morning for around 60 minutes to have a 120 ml blood sample taken. Furthermore the volunteers will fill out questionnaires and undergo nasal fluid collection and brushings. (see also **Table 3**)

Table 3: Time line procedures at Visit 2, 3 and 4

Time (Hr:min)		Procedure
00:00	Arrival	
00:05	Blood	Blood sample (120ml)
00:10	Questionnaires	mRQLQ, SMS, GE VAS
00:15	Pre-lavage	Secretion collection
00:20	Pre-lavage	Nasal brushings

00:25	Nasal-lavage	
00:55	Post-lavage	Secretion collection

GE VAS; Global Evaluation visual analogue scale

mRQLQ; miniRhinoconjunctivitis Quality of Life Questionnaire

SMS; Symptom Medication Score

At the start of May 2014, patients will receive the rescue medications (section 6.4.8.1) and will be asked to fill out the Global Evaluation (GE) VAS (**Appendix 4**), Symptom Medication Score (SMS) (**Appendix 5**) and mini-Rhinitis Quality of Life Questionnaire (mRQLQ) (**Appendix 3**) weekly until the end of July.

Visit 5:

Around 5 months after begin of AIT/placebo and during the pollen season participants will come to the hospital for 1.5 hours. During this visit the following will be undertaken (see also **Table 4**):

- A period of 15 minutes acclimatization to hospital environment and relative inactivity.
- Participants will mark questionnaires (**Appendix 3-5**) corresponding to symptoms and rescue medication use during the current pollen season.
- Furthermore the volunteers will undergo the same procedures as in Visit 0b, plus questionnaires and with the exception of the intradermal skin test and nasal challenge.

Table 4: Time line procedures at Visit 5

Time (hr:min)		Procedure
00:00	Arrival	
00:05	Blood	Blood sample (200ml)
00:15	Pre-lavage	GE VAS; mRQLQ; SMS, secretion collection
00:20	Pre-lavage	Nasal brushing
00:25	Nasal-lavage	
00:55	Post-lavage	Secretion collection

		Nasal biopsy
--	--	--------------

GE VAS; Global Evaluation visual analogue scale

mRQLQ; mini Rhinitis Quality of Life Questionnaires

SMS; symptom medication score

Visit 6:

After 6 months of treatment and shortly after the pollen season patients will mark a retrospective GE VAS (scale 0-100 mm; **Appendix 1**), the mRQLQ (**Appendix 3**) and complete a retrospective GE chart (**Appendix 2**) documenting the overall severity of their hay fever symptoms during the previous pollen season. Also a nasal allergen challenge with 5.000 BU/ml Timothy grass pollen allergen will be undertaken. We will record the Peak Flow as well as the response to challenge for one hour at 5, 15, 30 and 60 min with TNSS + VAS and PNIF.

Time (hr:min)		Procedure
-00:15	Arrival	TNSS+VAS; GE VAS, mRQLQ, GE, PNIF; Peak Flow
00:00	Nasal Challenge	5,000 BU/ml Timothy grass pollen allergen
00:05	Early Nasal response	TNSS + VAS; PNIF
00:15	Early Nasal response	TNSS + VAS; PNIF
00:30	Early Nasal response	TNSS + VAS; PNIF
01:00	Early Nasal response	TNSS + VAS; PNIF; PeakFlow

Visit 7:

After 12 months on treatment volunteers will attend the allergy unit for a period of 2 hours in the morning and 1 hour during the evening (3 hours). During this visit the same procedures as described at Visit 0b plus a blood sample of 200 ml will be undertaken (see also **Table 2**).

Non-atopic Participants:

Scheduled Visits (screening (Visit -1), one time point assessment (Visit 1):

Screening Visit – September 1st to November 30th, 2014.

Visit – 1 coinciding with Visit 7 at 12 months of treatment of the atopic participants, from December 1st 2014 to February 28th, 2015.

**Visit -1:
Screening visit:**

Volunteers will attend the allergy unit at the Royal Brompton Hospital for approximately 2 hours. During this visit the following will be undertaken:

- Written informed consent before any study procedures are performed.
- Demographic data (sex, date of birth, ethnic origin, medical history).
- Allergic history - record of presence/absence of previous allergic symptoms and medications taken by the subject.
- Physical examination and observations (weight, height, blood pressure, heart rate, peak expiratory flow rate, peak nasal inspiratory flow and spirometry).
- Completion of matching questionnaires to those completed by atopic participants at baseline: retrospective Global evaluation (GE) visual analogue scale (VAS) (scale 0-100 mm; **Appendix 1**), retrospective GE chart (**Appendix 2**), a Mini Juniper Rhinitis Quality of Life Questionnaire (mRQLQ) (**Appendix 3**) and Global evaluation scores (**Appendix 4 and 5**).
- Skin prick test - standard allergen test panel as described previously.
- Blood sampling of up to 20 ml for total IgE, specific IgE to Timothy grass pollen and total blood count will be taken.
- Recording of concomitant medication.
- Evaluation of inclusion and exclusion criteria.

Visit 1:

Non-atopic participants will be asked to attend for a morning visit (2 hours) and an evening visit (1 hour). They will be free to leave the hospital in between. This visit will be planned in order to coincide with the 12 month visit for the allergic participants. Participants will receive the following tests (see also **Table 5**):

- A period of 15 minutes acclimatization to hospital environment and relative inactivity.
- Blood sample of 200 ml.
- Participants will receive a nasal wash (lavage).
- Duplicate intradermal injections of 1.0 BU timothy grass allergen into the extensor surface of their right and left forearm, and a saline control injection also on the right arm will be performed. The EPR will be recorded at 15 minutes after injection; the LPR will be measured at 8 hours after injection.
- The participants will receive a nasal allergen challenge with 5,000 BU/ml Timothy grass pollen extract. The EPR after the nasal challenge will be recorded via the TNSS score (**Appendix 6**) and VAS score (**Appendix 7**) before challenge and after 5, 15, 30 and 60 minutes.
- Peak nasal inspiratory flow (PNIF) will be assessed shortly before collecting the nasal fluid before the nasal challenge and after 5, 15, 30 and 60 minutes after the nasal challenge.
- Peak expiratory flow (Peak Flow) will be assessed before nasal allergen challenge and 60 minutes after nasal allergen challenge.
- Nasal fluid will be collected by inserting a single foam sponge into each nostril and will be left in place for 2 minutes before removal. Secretions will be collected before challenge, at 5, 15, 30 and 60 minutes after nasal challenge and after 8 hours.
- The volunteers are allowed to leave the hospital (e.g. for work) and will return in the evening (after 8 hours) to allow reading of the skin LPR. Additionally, volunteers will undergo nasal brushings on both sides and a nasal biopsy. After the biopsy, volunteers will be observed for a further 30 minutes to ensure there is no nasal bleeding, and then allowed home.

- Food and non-caffeine-containing beverages (at room temperature) will be provided to all participants.

Table 5: Time line procedures at Visit 1 for the non-atopic participants

Time (hr:min)	*Participants will be allowed to leave and return at 8hours	Procedure
00:00	Arrival	
00:10	Blood	Blood sample (200 ml)
00:15	Pre Lavage	Nasal secretion collection and brushing
00:20	Nasal Lavage	Nasal lavage with 240 ml SinuRinse solution
00:25	Intradermal test	1BU intradermal inject to left and right forearm + saline injection
00:40	Intradermal test	EPR recorded at 15 minutes
00:50	Pre-Challenge	TNSS + VAS, PNIF, Secretion collection
00:55	Nasal Challenge	5,000 BU/ml Timothy grass pollen allergen
01:00	Early Nasal response	TNSS + VAS; PNIF; Secretion collection
01:10	Early Nasal response	TNSS + VAS; PNIF; Secretion collection
01:25	Early Nasal response	TNSS + VAS; PNIF; Secretion collection
01:55*	Early Nasal response	TNSS + VAS; PNIF; PeakFlow; Secretion collection
08:25*	Intradermal test	LPR
08:30		Secretion collection Nasal brushings Nasal biopsy

TNSS; total nasal symptom score

VAS; visual analogue scale

EPR; Early phase response

LPR; Late phase response

BU; Bioequivalent Unit

PNIF; Peak nasal inspiratory flow

GE VAS; Global Evaluation visual analogue scale

mRQLQ; mini Rhinitis Quality of Life Questionnaires

SMS; symptom medication score

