The study will be conducted over 44 months. We expect to screen 70 atopic patients in order to enroll up to 50 suitable atopic participants to ensure randomisation of at least 44 atopic participants following their baseline visit. Additionally, we shall recruit 20 healthy, non-atopic volunteers. Individuals with severe grass pollen hay fever, with or without associated seasonal asthma, will be recruited and screened after the pollen season from December 2013 to April 2014. Atopic Participants will undergo baseline assessments in January to April 2014. Screening assessments will be completed before eligible participants are randomized to active or placebo treatment. Atopic participants will then begin AIT treatment in January-April 2014 and continue treatment for 12 months. All atopic participants will be provided with anti-allergic rescue medications (antihistamine tablets, topical intranasal corticosteroids, and eye-drops) throughout the pollen season. Clinical surrogate endpoint assessments, plus blood, nasal fluid and nasal brushing sampling, will be performed at baseline, at around 4, 8 and 12 weeks after starting the AIT, and during the peak pollen season, at 6 months and at 12 months of treatment. Nasal mucosal biopsies will be taken at baseline, around 5 months, and 12 months of treatment. After 12 months of treatment, unblinding will take place. Those atopic participants receiving active AIT treatment will continue therapy for another 12 months followed by a withdrawal phase of 12 months. At 24 and 36 months (visit 8 and

9) all procedures and laboratory markers that were performed at 12 months (visit 7) (Fig.1) will be repeated for atopic participants on active treatment. Those atopic participants on placebo will be offered 24 months of active treatment after unblinding.

The healthy, non-atopic participants will undergo screening and one visit only, at 12 months, to coincide with the 12 month visit for the atopic participants. This visit will include clinical surrogate endpoint assessments, plus blood, nasal fluid, nasal brushing sampling, and nasal biopsies. The assessments will serve as a control for the results of the atopic participants at 12 months.

Figure 1: Study plan, atopic participants

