6.3.4 Withdrawal Criteria

Participants will be advised in the Informed Consent Form that they have the right to withdraw from the study at any time without prejudice. They may also be withdrawn from the study at the investigator's discretion at any time. Reasonable effort should be made to contact any participant lost to follow-up during the course of the study in order to complete assessments. Participants who prematurely leave the study will be asked to undergo an early termination visit. The data and blood, nasal fluids, nasal brushings and nasal biopsies collected before the withdrawal will be further processed and included in analysis. Participants who prematurely leave the study will not be replaced.

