6.3.8 Randomisation

After the screening phase eligible participants will be randomised, double-blind, to one of the two treatment arms in a 1:1 ratio and assigned a randomisation ID number. Additionally, the participant will be assigned a specific investigational medical product (IMP) kit, from those available at the site that corresponds to the treatment assignment. Each participant will be assigned a kit ID from the site's inventory whose treatment

matches the group to which the participant was randomized. The treatment assignment notification will be sent to authorized study personnel and the investigational pharmacy via email and/or fax. (The healthy, non-atopic control group will not be randomized to a treatment arm but investigators analysing biological samples from these participants will be blinded as to their origin.)

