6.4.3 Administration

The first Grazax® or Grazax® placebo will be administered under the supervision of the trial physician and the participant observed for one hour thereafter before discharge from the clinic. This will take place on Visit 1, which will be conducted 1 day after the

second baseline visit (V0b). Thereafter, home sublingual administration of Grazax® or Grazax® placebo tablets will occur daily during the 12 months of the trial. In those participants who received active treatment a continuation of daily treatment will take place for another 12 months. Those participants who received placebo will be offered 24 months of active treatment after completion of the first 12 months and after unblinding. Tablets should be removed from the blister packs with dry fingers and should be taken immediately after opening the blister. Each tablet should be placed underneath the tongue until fully dissolved (1–2 minutes). Swallowing should be avoided for about 1 minute. Food and beverage should not be consumed for the following 5 minutes. For additional information on the preparation and administration of Grazax®, please refer to the following uniform resource locator (URL):

http://www.grazax.com/SiteCollectionDocuments/Grazax.com/About%20Grazax/Grazax_SmPC_MRP_VAR13_15OCT2010.pdf

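### The Visit 0a text randomises before the two baseline visits, while the study design section and apparently the SAP schedule randomise later; following Visit 0a would put never-dosed leavers in the ITT set

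*Protocol*

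**What the plan says.** **Order of visits.** Protocol section 6.5.14 lists screening, then "Visit – 0a, after screening and before Visit 0b", then Visit 0b, then Visit 1. Visit 0a includes a 120 ml blood draw and nasal brushings. Visit 0b includes intradermal tests, the baseline nasal challenge with TNSS to 60 minutes, and a nasal biopsy. On the first tablet, section 6.4.3 says "This will take place on Visit 1, which will be conducted 1 day after the" second baseline visit.

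**Point of randomisation.**
- Protocol 6.5.14, Visit 0a: "Volunteers meeting the inclusion and exclusion criteria will be randomised into the two arms and will come in for 60 minutes".
- Protocol section 6, Study design: "enroll up to 50 suitable atopic participants to ensure randomisation of at least 44 atopic participants following their baseline visit".
- Protocol 6.3.8: "After the screening phase eligible participants will be randomised, double-blind, to one of the two treatment arms".
- SAP 10.2.1, schedule of assessments: the randomisation mark stands in the same position as the first mark for study tablets, which reads as Visit 1.

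**Analysis set.** Protocol 6.8.2 and SAP section 3 define ITT as everyone randomised, with no condition on dosing or on having an endpoint. Protocol 6.8.3.1 and SAP 7.2.1 use ITT for the primary endpoint. Protocol 6.3.4 adds: "Participants who prematurely leave the study will not be replaced". Protocol 6.8.2 invites people who drop out after randomisation to continue with assessments. The SAP gives no missing-data rule for the primary endpoint.

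**The concern.** The protocol gives two instructions on when allocation happens, and they cannot both be followed. The difference matters because the baseline visits are demanding, and a volunteer may well withdraw during them. If allocation comes after Visit 0b, such a person is simply an enrolled participant who was never randomised. If it comes before Visit 0a, the same person is a permanent member of the ITT set who never took a tablet and probably has no 12-month challenge.

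Two things are at stake. The first is the completeness of the primary analysis set. The second is what the target of at least 44 counts: people who start treatment, or people allocated before the most burdensome baseline procedures.

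**Working it through.** **1. Can the passages be reconciled?** The Visit 0a sentence has volunteers randomised and then attending for the Visit 0a procedures, so allocation precedes both baseline visits. Section 6 puts allocation after the baseline visit. It uses the singular and does not name Visit 0b, but any reading of it is later than the start of Visit 0a, so the two conflict. Section 6.3.8 says only that allocation follows screening. The baseline visits also follow screening, so it does not decide the matter. The SAP schedule must be read with care, because its column alignment is uncertain in the text read from the PDF: the intradermal row starts in the same position as the randomisation mark, although the protocol puts that test at Visit 0b. Whether the position is Visit 0b or Visit 1, it is later than Visit 0a.

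**2. Reproduce the plan's sample size.** Inputs from Protocol 6.8.1 are mean AUC 4.63, SD 1.65 and a 30% reduction. Alpha is 0.05. Sidedness is not stated, but two-sided reproduces the plan and one-sided does not (it gives 18 per group).
- Difference: 0.30 × 4.63 = 1.389.
- Standardised effect: d = 1.389 / 1.65 = 0.842.
- n per group = 2 × (1.960 + 0.842)² / d² = 2 × 7.85 / 0.709 = 22.1, rounded up to 23. The plan states 22. (The 0.842 inside the bracket is the normal quantile for 80% power; that it equals d is coincidence.)
- Power at 22 per group, normal approximation: Φ(0.842 × √(22/2) − 1.960) = Φ(0.83) = 79.7%. The plan states 80%.
- Power at 22 per group, two-sample t-test: 77.9%. With two groups this is the ANOVA of Protocol 6.8.3.1.

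**3. Effect of loss between randomisation and first dose.** The documents give no rate for this interval. I assume 0 to 6 people, taking the upper end from 50 − 44 = 6, split evenly between arms, with a complete-case analysis and no later attrition.

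If randomisation stops at 44:

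| Lost before dosing | Left per arm | Share of ITT undosed | t-test power | Normal approximation |
|---|---|---|---|---|
| 0 | 22 | 0% | 77.9% | 79.7% |
| 2 | 21 | 2/44 = 4.5% | 75.9% | 77.9% |
| 4 | 20 | 4/44 = 9.1% | 73.7% | 75.9% |
| 6 | 19 | 6/44 = 13.6% | 71.4% | 73.7% |

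If all 50 are randomised at Visit 0a and 6 are lost, (50 − 6)/2 = 22 per arm remain. Power is again 77.9% (t-test), but 6/50 = 12% of ITT is undosed.

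If 50 are enrolled, 6 leave during baseline and the remaining 44 are randomised after Visit 0b, there are also 22 per arm and power is 77.9%. None of those 6 is in ITT.

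**The case against.** The strongest reply is that this is one stray sentence. Section 6 and, as far as the table can be read, the SAP schedule both put allocation later, so staff would probably randomise after baseline anyway. Someone who leaves before the first tablet supplies no treated endpoint whenever allocation occurs, so timing changes the denominator more than the information. Losses before any tablet, under double-blinding, should not depend on arm. Visit 1 follows Visit 0b by one day, so most of the exposed time lies between Visits 0a and 0b.

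Most of this stands, and it limits the point to a reconciliation. It does not remove the point: the Visit 0a sentence is an operative visit instruction, and the section devoted to randomisation does not overrule it.

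A reader might also infer more than the documents support:
- **That section 6.3.8 also randomises before baseline.** It fits either order.
- **That people lost at baseline have neither a baseline nor a 12-month TNSS.** Anyone who completes the Visit 0b challenge has a baseline value, and all dropouts are invited to continue. A missing 12-month value is likely, not certain.
- **That the plan budgets 12% loss between randomisation and dosing.** In section 6 the gap from 50 to 44 is over-enrolment ahead of randomisation. Applying 12% after stopping at 44 uses the loss but discards the six extra enrolments meant to cover it.
- **That the SAP shares the fault.** It appears already to carry the later timing.

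**Conclusion.** The inconsistency is real. The Visit 0a text contradicts section 6 of the protocol and appears to contradict the SAP schedule, and section 6.3.8 does not settle it. If the Visit 0a text were followed, the ITT definition and the no-replacement rule would put never-dosed leavers into the primary analysis set, probably without a 12-month TNSS.

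The size is uncertain. A fall in t-test power from 77.9% to 71.4% is the far end of an assumed range: it needs randomisation to stop at 44 and six people then to be lost. If all 50 are randomised and six lost, power does not change and the cost is 12% of ITT undosed. It would be tempting to call this a source of bias or a definite loss of power. The documents support neither: pre-dose losses under blinding should be unrelated to arm, and the power loss depends on how many are randomised. What is supported is avoidable missing ITT data, possible loss of precision and an unclear ITT denominator. The correction is a free improvement.

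**What to change.** Remove the randomisation clause from the Visit 0a sentence in Protocol 6.5.14, leaving only the attendance and procedures. State in section 6.3.8 that randomisation and kit assignment take place once Visit 0b is complete and before the first tablet at Visit 1. Confirm that the randomisation mark in SAP 10.2.1 sits at that point. If it already does, the SAP needs no change.

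This is a wording change. It adds no visits or procedures and leaves the sample size alone. Kit assignment moves later, into the one-day interval between Visit 0b and Visit 1 or to Visit 1 itself, so the pharmacy must be able to release a kit in that time. Section 6.3.8 already draws kits from site stock with notification by email or fax.

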6.2.1 Secondary endpoints

1. Cross-sectional area in cm² of EPR and LPR skin responses to intradermal grass pollen allergen injection at 12 months in active versus placebo treated participants.
2. Serum and nasal fluid grass pollen specific IgG4 level and inhibition of B cell IgE-facilitated allergen binding in active versus placebo-treated atopic patients versus non-atopic controls at 12 months.
3. Allergen-induced peripheral blood basophil activation in active versus placebo-treated atopic participants versus non-atopic controls at 12 months.

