6.6.1 Flow Cytometry

Flow cytometry for analysis of basophils will be performed on fresh blood samples, on the same day as venesection. All other flow cytometry will be performed on stored peripheral blood mononuclear cells (PBMCs), isolated from whole blood by layering over a Ficoll cushion, centrifuging and harvesting the buffy coat layer. PBMCs will be stored at -80°C before thawing and analysis in batches to reduce variability.

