7. ENDPOINT EVALUATION

7.1 Overview of Efficacy Analysis Methods

7.1.1 Assessment Time Windows

All study visits must occur within the time limits specified below:

Atopic

Phase I (all):

Screening Visit – Visit -1, from December 2013 to April 2014

Visit – 0a, after screening and before Visit 0b

Visit - 0b, from January 2014 to April 2014

Visit – 1, after Visit – 0b

Visit – 2, from February to May 2014

Visit – 3, from March to May 2014

Visit – 4, from April to June 2014

Visit – 5, from May to August 2014

Visit – 6, from July to October, 2014

Visit – 7, from January to April 2015

Phase II (active treatment group only)

Visit – 8, 24 months after start of treatment

Visit – 9, 36 months after start of treatment

Non-Atopic

Screening Visit – September 1st to November 30th, 2014

Visit – 1 coinciding with Visit 7 at 12 months of treatment of the atopic participants

Unscheduled visits may also occur throughout the study.

The pollen season will be defined as in the protocol. Pollen counts will be quantitated retrospectively for the purposes of analysis. *Pollen season* is defined as follows:

Start of season	First 3 consecutive days at pollen count >10 grains/cm ³
End of season	First 3 consecutive days at pollen count < 10 grains/cm ³
Start of peak season	First 3 consecutive days at pollen count >30 grains/cm ³
End of peak season	First 3 consecutive days at pollen count < 30 grains/cm ³

A variable for the pollen season and peak pollen season (0 = no pollen season, 1 = pollen season, 2 = peak pollen season) will be created by the AIT team indicating when the season started and finished.

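### The non-atopic control visit is said to coincide with Visit 7, but its dated window overlaps only 59 of Visit 7's 120 days

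*Protocol*

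**What the plan says.** Protocol 6.5.14 gives the control visit as "Visit – 1 coinciding with Visit 7 at 12 months of treatment of the atopic participants, from December 1st 2014 to February 28th, 2015" and states the intention again in its description of that visit: "This visit will be planned in order to coincide with the 12 month visit for the allergic participants". For atopic participants the same section lists "Visit – 7, from January to April 2015". That fits the treatment dates in protocol section 6 (Study design): "Atopic participants will then begin AIT treatment in January-April 2014 and continue treatment for 12 months".

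SAP 7.1.1 repeats the Visit 7 window but gives the control visit only as "Visit – 1 coinciding with Visit 7 at 12 months of treatment of the atopic participants", with no calendar dates. The protocol asks for the atopic windows to be kept where possible; SAP 7.1.1 makes its windows mandatory.

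Three further statements decide how much the dates matter:

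- Protocol 6.2.1 makes a comparison with controls a secondary endpoint: "Allergen-induced peripheral blood basophil activation in active versus placebo-treated atopic participants versus non-atopic controls at 12 months".
- Protocol 6.6.1 states "Flow cytometry for analysis of basophils will be performed on fresh blood samples, on the same day as venesection". All other flow cytometry in that section is run in batches on stored cells.
- Protocol 6.3.8 states that "investigators analysing biological samples from these participants will be blinded as to their origin".

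**The concern.** The protocol's dates do not deliver the coincidence it promises. Treatment starts no earlier than January 2014, so no 12-month visit is scheduled in December 2014, when controls may be seen. Anyone who starts in March or April 2014 reaches 12 months after the control window has closed.

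Two things are at stake. The first is the comparison with controls on measurements made on the day of the visit. For stored samples, batching can separate assay date from visit date. For fresh-blood basophil activation the two dates are the same, so any change over time in reagents, instrument settings or operators could be partly mixed with the difference between atopic and control participants. The same applies in principle to other same-day measurements for which SAP 7.2.1 and 7.3 plan a three-group comparison: TNSS after challenge, peak nasal inspiratory flow and skin responses.

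The second is the blinding of sample origin, because some dates are possible for one group only.

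**Working it through.** There is no stated figure to reproduce. The check is an inclusive count of calendar days.

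**Inputs**
- Control window (protocol 6.5.14): 1 December 2014 to 28 February 2015.
- Visit 7 window (protocol 6.5.14 and SAP 7.1.1): January to April 2015, taken as full months, 1 January to 30 April.
- Control screening (protocol 6.5.14): 1 September to 30 November 2014.
- Group sizes: 20 controls; at least 44 randomised atopic participants.

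**Lengths and overlap**
- Control window: 31 + 31 + 28 = 90 days.
- Visit 7 window: 31 + 28 + 31 + 30 = 120 days.
- Shared period, 1 January to 28 February: 31 + 28 = 59 days.
- Shared part of the Visit 7 window: 59/120 = 49.2%.
- Shared part of the control window: 59/90 = 65.6%.
- Days that can hold only controls (December): 90 − 59 = 31.
- Days that can hold only Visit 7s (March and April): 120 − 59 = 61.
- Window midpoints: 14 January and 1 March 2015, about 6.5 weeks apart.

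**Participants outside the shared period, if visits were evenly spread (an assumption)**
- Controls: 20 × 31/90 = 6.9, about 7.
- Atopic participants: 44 × 61/120 = 22.4, about 22.
- With 50 atopic participants: 50 × 61/120 = 25.4, about 25.

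The documents give no distribution of visits within the windows, so the range for each count runs from none to all.

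**Can booking within the present windows cure it?** Only in part. Putting all 20 controls in January and February removes the December problem. It provides no control in March or April, and the atopic visits cannot be moved freely because the start of treatment fixes the 12-month date.

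**Longest gap from control screening to the control visit**
- Present window: 1 September 2014 to 28 February 2015 = 180 days.
- Window extended to 30 April 2015: 180 + 31 + 30 = 241 days.

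**The case against.** The strongest reply is that the windows permit a mismatch without imposing one. Two thirds of the control window lies inside the Visit 7 window, and the protocol tells staff to plan the control visit to coincide with the 12-month visit. A reader might infer that the controls are simply not concurrent. The documents do not support that: every control could be booked in January or February without a deviation. What remains is that such booking still leaves March and April without controls.

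A reader might also infer that the blind on sample origin is broken. That goes too far. January and February dates reveal nothing, and other dates reveal origin only to someone who sees them. The documents do not say whether analysts do. Exposure is most plausible for the same-day basophil assay and least so for batched stored samples. The atopic windows are also soft in the protocol, so the rule that a given month belongs to one group is not absolute.

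Confounding by season is a third tempting reading. Both windows fall before the grass season, which the protocol places in mid-May to mid-July. Atopic participants with symptoms outside that season are excluded, as are controls with any seasonal symptoms (6.3.3). No clear seasonal mechanism is left.

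Assay drift is a possibility, not something the documents report. Fresh basophil assays already run from baseline to 12 months, a far longer span than 6.5 weeks. Finally, the stakes are modest: both documents treat secondary analyses as supportive, and the SAP lists basophil activation under mechanistic assessments (7.3.2). These points limit the size of the problem. They do not remove the contradiction in the dates.

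**Conclusion.** The protocol is wrong as written, with low severity. Its two windows do not coincide, and the undated wording in the SAP does not settle which dates apply. The day counts are firm, given full calendar months: 59 shared days, 31 for controls only and 61 for Visit 7 only. The participant counts are not firm, because they rest on an assumed even spread.

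The consequence is a possible, unquantified and partial confounding with assay date in non-randomised comparisons that use same-day measurements, together with a possible weakening of the blind on control or atopic origin. A date never separates active from placebo, so the primary randomised comparison and its blind are untouched. The point is more than clerical, because the control group is there to provide a concurrent 12-month reference and fresh assays cannot be re-run together later.

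**What to change.** Set the non-atopic Visit 1 window in protocol 6.5.14 to January to April 2015, put the same dates in SAP 7.1.1, and spread the control visits across the period in which Visit 7s take place.

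This needs the same 20 controls, one visit each and no new procedure. The cost is that control visits may finish up to two months later. The longest gap from control screening to the visit also rises from 180 to about 241 days, unless the screening window is moved too.

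If controls have already been seen in December, report the fresh-blood comparison with controls restricted to January and February visits as a sensitivity analysis, and note its lower precision. With evenly spread visits it would keep about 13 of 20 controls (20 × 59/90 = 13.1) and about 22 of 44 atopic participants (44 × 59/120 = 21.6).
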